2.2 Investigational Device

The WCD used for this study will be a configuration controlled by the Sponsor from managed inventory designated for clinical evaluations only. The devices will be production-equivalent systems with shock alarms disabled (Shock Alarm Event Markers will be recorded by the device for analysis purposes), defibrillation therapy programmed OFF, and detection parameters at default settings. Detection parameter default settings include Ventricular Tachycardia (VT) rate threshold at 170 bpm and Ventricular Fibrillation (VF) rate threshold at 200 bpm.

The ASSURE™ Cardiac Recovery System is comprised of several components:

- A WCD including a Garment with embedded ECG sensors that is worn on the body next to the skin, a Monitor which houses the battery and the graphic user interface, Cable Assembly which connects the Garment to the Monitor, and a Carry Pack
- A Charger that allows recharging of the monitor batteries
- A Tablet that allows the WCD to be programmed via wireless connection to the Monitor
- CareStation™ website which allows users to view WCD data associated with study subjects
- An ASSISTANT™ mobile device that allows data uploads from the WCD to CareStation website

3. Study Objectives

Primary: To evaluate ambulatory detection performance of the ASSURE Wearable Cardioverter Defibrillator (WCD)

Secondary: To evaluate arrhythmia detection performance and safety of the ASSURE WCD CONFIDENTIAL INFORMATION - This material constitutes confidential and proprietary information of Kestra Medical Technologies. This material may not be distributed, reproduced, or divulged without the written consent of Kestra Medical Technologies.

4. Endpoints and Hypotheses

The endpoint analyses will be performed after all subjects have either completed the final visit or withdrawn early from the study, the study database has been cleaned, verified and locked, and adjudication/reconciliation of all episodes has been completed.

4.1 Primary Endpoint

The primary endpoint is the WCD False Positive Alarm (FPA) Rate calculated as False Positive Alarms per subject-day where days per subject will be calculated by taking the total wear time in minutes as recorded in the eCRF by the Research Coordinator from the CareStation remote monitoring system divided by 1,440 minutes. The study will be considered successful if the WCD FPA Rate is less than 0.29 FPAs per subject-day.

The hypotheses to be tested are as follows:

 H_0 : $p_1 \ge 0.29^1$ H_1 : $p_1 < 0.29^1$

where

p₁ = ASSURE False Positive Alarm Rate

4.2 Sample Size Estimation

The following assumptions were used to determine the sample size for the primary endpoint of WCD False Positive Alarm Rate:

- The primary analysis is a one-sided comparison of the WCD FPA rate per subject-day against the value of 0.29
- The WCD FPA rate is expected to be 50% lower than 0.29
- At least 90% power is considered sufficient
- The statistical test will be performed with a 2.5% significance level
- Average wear time per subject, per day, is 14 hours
- The FPA rate has a Poisson distribution with variance to mean ratio, ρ , = 14 and an intra-site correlation =0.026.²
- For large total number of expected events, the Poisson (λ) distribution is approximately normally distributed as N (μ = λ , σ^2 = $\rho^*\lambda$).

To maintain at least 90% power to detect a FPA rate 50% lower than 0.29 a sample size of approximately 105 subjects is necessary. However, the study will enroll at least 130 subjects to increase the likelihood that a subject will experience a true ventricular arrhythmic event.

Sample size calculations were performed using the R statistical package.

4.3 Secondary Endpoints

True Positive Detection:

¹ Equivalent to one false alarm every 3.43 subject days (2.0 per subject week of use) as cited in LifeVest Model 4000 Operator's Manual, Rev C; 7-5.)

² Estimates based upon sponsor study 'Electrocardiogram (ECG) Recordings from Cardiac Patients during Ambulatory Use with Assure™ Prototypes', protocol 3330766, September 2017.

CONFIDENTIAL INFORMATION - This material constitutes confidential and proprietary information of Kestra Medical Technologies.

This material may not be distributed, reproduced, or divulged without the written consent of Kestra Medical Technologies.

The incidence of WCD True Positive Detections will be summarized for each adjudicated episode (see Appendix A for format of episode summary). Additional details are found in the Section 10. Definitions.

- Missed Events (False Negative Detections):
 The incidence of WCD Missed Events (False Negative Detections) for each adjudicated episode will be summarized (see Appendix A for format of episode summary). Additional details are found in the Section 10. Definitions.
- Estimated Inappropriate Shock Rate:
 An estimate of the Inappropriate Shock Rate, per

An estimate of the Inappropriate Shock Rate, per subject-day, will be calculated as the product of the WCD FPA rate and the Missed Shock Alarm Rate where the WCD FPA rate, per subject-day is estimated from the primary endpoint of this study, and the Missed Shock Alarm Rate is estimated as the upper limit of the 95% confidence interval of 23.1% based on data from two previous studies (GDR 3333597 ASSURE UISim Sleep Study and GDR 3334121 ASSURE UISim 7-day study). See the protocol for additional information.

Adverse Events Determined to Be at Least Possibly Related to the Device:
 Summary of adverse events that are determined to be at least possibly related to the device.

Other measures, for consideration of future investigation, include, but are not limited to, average daily wear time, which will be calculated for each subject, overall wear time, with the first and last day of the study not included, BORG Comfort Scale, and a Usability Survey.

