- Protocol 3333597: Single center (Swedish Sleep Medicine Sleep Lab) randomized study to assess subject response time to high priority alerts (shock alarms) during one night's sleep. Subjects were randomized at enrollment to one of 12 simulated alarm scenarios. 12 subjects from the general population were enrolled (5 males/ 7 females) with average age of 69 (range 43-73). 24 shock alarms were issued (2 to each subject). Mean response time to shock alarm

during sleep was $(7.0 \pm 2.5 \text{ seconds})$. There was one shock alarm that was "missed" (subject failed to respond in 20 seconds or less). No AEs were reported.

Protocol 3334121: Single center randomized study to assess subject response time to high priority alerts (shock alarms) during normal daily activities. Subjects were randomized to one of three simulated alarm scenarios implemented over a 7-day wear period. 20 subjects from the general population were enrolled (9 males/11 females) with average age of 57 (range 41-71). 55 shock alarms were issued. Mean response time to shock alarm during normal daily activities was 13.3 ± 10.1 seconds. There were eleven shock alarms that were "missed" (subject failed to respond in 20 seconds or less). One minor AE reported (skin irritation).

Fourth Generation Prototypes:

Protocol 3335586: Multicenter (3) non-randomized study to evaluate safety and detection performance of the ASSURE wearable cardioverter defibrillator (WCD) device during a typical 30-day prescription period; 32 subjects enrolled in the US from the general population (16 females, 16 males, average age 61.7, age range 40-73). This was a pilot study for the pivotal clinical study (ACE-DETECT). 8 AEs were reported in 6 subjects (2 subjects experienced 2 AEs each). 7 AEs were related to skin irritation and 1 was scratches from the garment seam; All 8 were minor severity.

Study Rationale

A WCD provides continuous arrhythmia monitoring with detection of potentially fatal ventricular arrhythmias and automatic defibrillation. The ASSURE WCD incorporates an automatic Rhythm Analysis Algorithm (RAA) that uses patient ECG to determine if a patient should be treated with a defibrillation shock. The device also provides vibratory, audible, and visual alerts to the patient when a shockable rhythm is detected and before a shock is delivered. If the patient is conscious during this "shock alarm", they will be able to defer a shock using a divert button on the WCD.

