An estimate of the inappropriate shock rate will be calculated as the product of the WCD False Positive Alarm Rate (the Primary Outcome measure of this study) and the Missed Shock Alarm Rate. The Missed Shock Alarm Rate was derived from two prior studies during which high priority alarms (shock alarms) were delivered randomly to study subjects. A "Missed Shock Alarm" was one during which the subject failed to respond to the shock alarm within 20 seconds following alarm activation. Data was obtained both during sleep (GDR 3333597 ASSURE UISim Sleep Study) and during normal daily activities (GDR 3334121 ASSURE UISim 7-day study).

Adverse Events

AEs will be summarized using the SAF subject set. Separate summaries of AEs at least possibly related to device use and by severity (as reported by the Investigator and reviewed by the Medical Monitor) will be prepared. UADEs will also be summarized. AEs leading to withdrawal from the study will be listed and tabulated.

Subgroup Analysis

Subgroup analyses are exploratory and will be specified in the Statistical Analysis Plan.

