5.1 Primary Endpoint

A random effects Poisson regression model will be fit with the number of FPAs for each patient as the outcome variable, the logarithm of days of wear as an offset term, and a random site effect. The fitted model will be used to calculate a two-sided 95% confidence interval for the FPA rate of the study device. The null hypothesis will be rejected if the upper bound of the 95% confidence interval is less than the rate reported for the comparator device (0.29). Note that a two-sided 95% confidence interval corresponds to a two-sided test with significance level 0.05 or a 1-sided test with significance level 0.025.

If the null hypothesis is rejected, the conclusion will be that the FPA rate for the WCD study device is significantly lower than the rate reported for the comparator device.

Assumptions regarding the Poisson regression model will be checked by assessing for example the deviance and goodness of fit statistics and dispersion. If substantive violations of model assumptions are suspected, a sensitivity analysis will be performed using the bootstrap method with resampling of cases. Ten thousand bootstrap samples will be created, and confidence intervals will be constructed by the percentile method. In the event there are significant violations of model assumptions for the Poisson regression model, the bootstrap confidence interval will be utilized to test the hypotheses on the primary endpoint.

An additional random effects Poisson regression model will be fit including patient characteristics (including age, gender, BMI, baseline QRS width, and ICD type) as covariates in an exploratory analysis to determine whether any of the anticipated covariates influences the estimate of FPA rate.

The primary endpoint will also be summarized as the median FPA rate, and the percentage of subjects with at least one FPA will be reported. If subjects have more than one FPA, the distribution of number of FPAs per subject may also be reported.

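### The estimated inappropriate shock rate in SAP 4.3 uses a disclosed upper limit (23.1%) for one factor and plans neither a central figure nor an interval for the product: a minor reporting gap that is cheap to close

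*SAP*

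**What the plan says.** SAP 4.3 describes an estimate, per subject-day, formed as the product of two factors. The first is the FPA rate estimated from the primary endpoint. For the second, "the Missed Shock Alarm Rate is estimated as the upper limit of the 95% confidence interval of 23.1"%, based on the sleep study (3333597) and the 7-day study (3334121). Protocol section 12 gives the same product but says only that "The Missed Shock Alarm Rate was derived from two prior studies"; it does not mention an upper limit.

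The counts are in Protocol section 6. In the sleep study "24 shock alarms were issued (2 to each subject"), and one was missed. The 7-day study, run during normal daily activities, issued 55 alarms to 20 subjects. "There were eleven shock alarms that were" missed.

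For the FPA rate itself, SAP 5.1 states: "The fitted model will be used to calculate a two-sided 95% confidence interval for the FPA rate of the study device". If model assumptions fail, "Ten thousand bootstrap samples will be created, and confidence intervals will be constructed by the percentile method". Nothing in SAP 4.3, 5.1, 5.2 or 5.3 carries that uncertainty into the shock-rate product. SAP 5.2 makes all secondary endpoints exploratory, with no performance criteria.

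**The concern.** Multiplying an estimate by an upper confidence limit gives a hybrid. It sits above the centre because one factor is pushed up, yet it carries none of the sampling error of the other factor. A reader who sees one number called an estimate cannot tell the likely rate or how uncertain it is.

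Shock alarms and shocks are disabled in this trial, so the product is its only figure for how often patients would be shocked inappropriately. The study is also meant to support a premarket application (Protocol section 6). What is at stake is how this one figure is reported and used. No test or success criterion depends on it.

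**Working it through.** **1. Reproduce 23.1%.** Pooled missed alarms: (1 + 11)/(24 + 55) = 12/79 = 0.1519. The two-sided 95% Wald upper limit is 0.1519 + 1.96 × √(0.1519 × 0.8481/79) = 0.2310, which matches. Other two-sided 95% limits on 12/79 do not: Jeffreys 24.3%, Wilson 24.7%, Agresti-Coull 24.9%, exact 25.0%. The SAP names no method, so Wald is an inference. If it was used, 79 alarms in 12 + 20 = 32 people were treated as independent.

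**2. Size of the shift.** 0.231/0.1519 = 1.52, so the product is 52% above the pooled value whatever the FPA rate turns out to be. Against the 7-day study alone (11/55 = 20.0%), the ratio is 0.231/0.20 = 1.155. The sleep study alone gives 1/24 = 4.2%.

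**3. Planning inputs (SAP 4.2 unless stated).**
- FPA rate 50% below 0.29, i.e. 0.145 per subject-day.
- "The FPA rate has a Poisson distribution with variance to mean ratio" 14, and intra-site correlation 0.026.
- "Average wear time per subject, per day, is 14 hours".
- 130 subjects, 30 days and, as an assumption, 10 equal sites of 13.
- A subject-day is 1,440 minutes worn (SAP 4.1), so 30 subject-days are 720 worn hours, not a 30-day prescription.

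**4. FPA precision.** Wear: 130 × 30 × 14/24 = 2,275 subject-days; 2,275 × 0.145 ≈ 330 FPAs. SE = √(14 × 330)/2,275 = 0.0299, or 21% of the rate. With site design effect 1 + 12 × 0.026 = 1.312, SE = 0.0342 (24%). The 95% CI is 0.145 ± 1.96 × 0.0299 = 0.0865 to 0.2035 (0.0779 to 0.2121 with the site effect).

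**5. Products at an FPA rate of 0.145.** The last column is 30 calendar days at 14 h/day, i.e. 17.5 subject-days.

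| Missed-alarm rate | Per 30 subject-days | Per 30 calendar days |
|---|---|---|
| 23.1% (SAP) | 0.145 × 0.231 × 30 = 1.00 | 0.59 |
| 12/79 (pooled) | 0.145 × 0.1519 × 30 = 0.66 | 0.39 |
| 11/55 (7-day study) | 0.145 × 0.20 × 30 = 0.87 | 0.51 |

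**6. Interval carrying both sources.** The relative variance of the FPA rate is 0.206² = 0.042 (0.056 with the site effect). That of the missed-alarm rate is (1 − p)/(np) = 0.8481/12 = 0.071. FPA error is therefore 38% to 44% of the total, and SAP 4.3 carries none of it. One million draws of a gamma FPA rate times a binomial missed-alarm proportion give these 95% percentile intervals per 30 subject-days, with usability alarms independent:
- around 0.66: 0.29 to 1.17 (0.28 to 1.21 with the site effect);
- around 0.87: 0.38 to 1.54 (0.36 to 1.59).

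The upper limit around 0.66 depends on the scale: 1.10 (1.12 with the site effect) by the linear delta method and 1.28 (1.33) on the log scale. All are above 1.00.

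**7. What the planned outputs already allow.** Multiplying the FPA limits from step 4 by 0.231 × 30 gives 0.60 to 1.41 (0.54 to 1.47 with the site effect). In simulation with independent alarms and a true missed-alarm rate of 15.2% or 20%, the upper end fell below the true product about 1% of the time. It is a usable conservative bound, and it takes one multiplication.

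**The case against.** The strongest reply is that an upper limit is a sensible, openly stated choice for a harm measure. The missed-alarm data come from 32 general-population subjects responding to simulated alarms on third-generation prototypes, whereas this trial enrols cardiac patients. A sampling interval around 12/79 does not cover that difference. The counts are printed in the protocol, to which SAP 4.3 refers the reader, and the FPA interval is a primary output, so anyone can rebuild the pieces. All of this stands. It is why the 23.1% figure should be kept and not replaced by a lower headline value.

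It does not settle the matter. Conservatism in one factor neither shows the centre nor covers error in the other, and the protocol's wording would lead a reader to expect the rate itself rather than its upper limit.

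A reader might infer more than the documents support:
- **That the SAP offers the product as a 95% upper bound and the bound fails.** It makes no such claim, so its coverage as a bound is not a defect.
- **That 23.1% is an error or concealed.** It reproduces from the counts and is labelled as a limit.
- **That the planned outputs cannot give a bound.** Step 7 of the working shows that they can.
- **That 11/55 is a waking-hours rate.** The protocol says normal daily activities over a 7-day wear period, and says no more than that.

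**Conclusion.** The point holds as a minor reporting improvement. The single planned figure is 52% above the pooled value, yet at planning values it lies below the upper 95% limit of the product (1.00 against 1.17 to 1.21 per 30 subject-days). It is therefore neither a central estimate nor a 95% upper bound.

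The 52% rests only on the documents' counts. The rates and intervals rest on the SAP's planning values, on equal sites of 13, and on independent usability alarms. The documents give no basis for sizing within-subject clustering of those alarms; positive clustering would widen the interval. The primary hypothesis test and the study's success criterion are untouched.

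**What to change.** In SAP 4.3:

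- **Keep the 23.1% product**, label it conservative, and name the interval method behind the limit.
- **Add a central estimate beside it**: FPA rate × 12/79, with FPA rate × 11/55 as the less favourable study-specific value. State that the pooled rate reflects the 24:55 mix of alarms in the two usability studies, and that these used general-population subjects and simulated alarms.
- **Give a 95% interval carrying both sources of error.** For the FPA rate, use whichever method supplies the primary interval: the model-based one, or the bootstrap if SAP 5.1 invokes it. Combine it with the binomial uncertainty of the missed-alarm counts, clustered by subject where subject-level data are held. Otherwise state that clustering is not covered.
- **At minimum**, report the SAP 5.1 confidence limits multiplied by 23.1%, and present the upper end as a labelled conservative upper bound.
- **State the unit**: a subject-day is 1,440 worn minutes.

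SAP section 9 allows such a change by amendment before the primary endpoint is analysed. The cost is wording and a little programming; the clustered version also needs the sponsor's usability data. The reported upper limit will be less favourable than the single figure now planned.

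### The 23.1% upper limit for the Missed Shock Alarm Rate (SAP 4.3) treats 79 alarms from 32 enrolments as independent, so it is too low if misses cluster within subjects (low impact)

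*SAP*

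**What the plan says.** SAP 4.3 defines the Estimated Inappropriate Shock Rate per subject-day as the false positive alarm (FPA) rate from this study times a Missed Shock Alarm Rate from two earlier sponsor studies. It fixes the second factor: "the Missed Shock Alarm Rate is estimated as the upper limit of the 95% confidence interval of 23.1" per cent. It names the two studies but gives no counts, point estimate or interval method, and adds "See the protocol for additional information".

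The counts are in protocol section 6, Previous Clinical Studies:

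- Sleep study, 12 subjects: "24 shock alarms were issued (2 to each subject"), and "There was one shock alarm that was" missed.
- Seven-day daily-activity study: "20 subjects from the general population were enrolled (9 males/11 females"); "55 shock alarms were issued"; "There were eleven shock alarms that were" missed.

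Protocol section 12 describes the same product but does not mention an upper limit. SAP 5.2 states that secondary endpoints are exploratory and carry no performance criterion.

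**The concern.** The constant goes straight into a named secondary endpoint, so any error in it passes in full proportion into the reported shock rate. An upper limit rather than the observed proportion makes sense only as deliberate caution, and it gives that caution only if the limit is wide enough for the data behind it. Each subject in the earlier studies received several alarms. A person who sleeps heavily or reacts slowly may miss more than one, so repeated alarms can carry less information than the same number from different people. A limit that ignores this is too narrow, in the direction that flatters the device.

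**Working it through.** **Inputs.** Protocol section 6: 1 missed of 24 asleep (12 subjects, 2 alarms each); 11 missed of 55 awake (20 subjects). SAP 4.2: comparator rate 0.29 and expected rate 50% lower, so a planning FPA rate of 0.5 × 0.29 = 0.145 per subject-day.

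**1. Reproduce 23.1%.** Pooled p = (1 + 11)/(24 + 55) = 12/79 = 0.1519. SE = √(0.1519 × 0.8481/79) = 0.0404. Two-sided 95% Wald upper limit = 0.1519 + 1.96 × 0.0404 = 0.2310. This matches the SAP to the digit. The SAP names no method, so Wald with n = 79 independent alarms is inferred from the match.

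**2. Allow for clustering, keeping Wald.** The documents give no within-subject correlation, so the intraclass correlation (ICC) is an assumption. Two more are needed: that nobody took part in both studies, and that the 55 awake alarms were split as evenly as possible (15 subjects with 3, 5 with 2). An even split gives the smallest design effect for 20 subjects.

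- Size-weighted mean alarms per subject = Σm²/Σm = (12×4 + 15×9 + 5×4)/79 = 203/79 = 2.57.
- Design effect = 1 + (2.57 − 1) × ICC.
- Upper limit = 0.1519 + 1.96 × 0.0404 × √(design effect).

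| ICC (assumed) | Design effect | Wald upper limit | Product at FPA 0.145 |
|---|---|---|---|
| 0 (SAP) | 1 | 23.1% | 0.0335 |
| 0.1 | 1.157 | 23.7% | 0.0344 |
| 0.3 | 1.471 | 24.8% | 0.0359 |
| 0.5 | 1.785 | 25.8% | 0.0374 |

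**3. Choice of interval, without clustering.** Two-sided 95% upper limits for 12/79 are 24.3% (Jeffreys), 24.7% (Wilson) and 25.0% (Clopper-Pearson); products at 0.145 are 0.0352, 0.0358 and 0.0363. A two-sided 95% interval should have its upper limit below the true rate about 2.5% of the time. With n = 79 and a true rate of 20%, the Wald limit falls below 20% whenever there are 10 or fewer misses, which has binomial probability 6.3%; for Wilson the corresponding figure is 1.5%. Averaged over true rates from 10% to 25%, the figures are about 5% for Wald and 2% for Wilson.

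**4. Both together.** A Wilson limit on the effective sample size (79 divided by the design effect: 68.3 at ICC 0.1 and 44.3 at ICC 0.5) is 25.5% and 28.5%; the products are 0.0370 and 0.0413. This range mixes the two effects, so it does not measure clustering alone.

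**5. Scale.** At the point estimate the product is 0.145 × 0.1519 = 0.0220. SAP 4.2 planning values with 130 subjects and 30 days imply 130 × 30 × 14/24 × 0.145 ≈ 330 false alarms. With a variance-to-mean ratio of 14, the 95% half-width on the FPA factor is 1.96 × √(14/330) ≈ 0.40, or 40%, before intra-site correlation.

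**The case against.** The strongest reply is that nothing here is wrong as a sum. The figure, its label and the protocol's counts agree, and Wald is a standard interval. That stands. A reader might infer that the SAP miscalculated, or that every standard 95% limit lies between 24.3% and 25.0%. The documents support neither, since a standard method gives exactly 23.1%.

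It is also fair that Wald against Wilson, taken alone, is a preference. With 12 misses and 67 responses the usual large-sample conditions are met, and the alternatives differ among themselves by 0.7 points.

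The size of the clustering effect rests on assumptions. The two studies also had different miss rates (4.2% and 20.0%), and stratifying by study cuts the variance by about 4%, for a Wald limit of 22.9%. That is a small offset. It limits the size of the problem but does not justify treating repeated alarms as independent.

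A one-sided 95% bound would be 22.7% to 23.4% (Jeffreys to Clopper-Pearson), so 23.1% would fit that reading before clustering. But the SAP calls it the limit of a 95% confidence interval, and for the primary endpoint SAP 5.1 says "The fitted model will be used to calculate a two-sided 95% confidence interval for the FPA rate of the study device".

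Lastly, the SAP openly says that it uses an upper limit, and 23.1% exceeds both the pooled 15.2% and the awake 20.0%. That is a legitimate cautious choice. What remains is that the limit is less cautious than its label.

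**Conclusion.** The concern holds in a limited form. The 23.1% is correctly computed for independent alarms, but the 79 alarms came from 12 + 20 enrolments, and any positive within-subject correlation puts the matching limit higher. Under an assumed ICC of 0.1 to 0.5, no subject overlap and an even split, the Wald limit becomes 23.7% to 25.8%, which is 3% to 12% higher in relative terms (23.7/23.1 and 25.8/23.1). The documents cannot say where in that range, or outside it, the true figure lies. The low placement of the Wald limit adds to the problem: other methods give 24.3% to 25.0% before clustering, 5% to 8% higher in relative terms.

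Impact is low. The shift is small beside the roughly 40% half-width on the FPA factor, the endpoint has no performance criterion, and the primary test and sample size do not use the number. It would be wrong to infer that the true miss rate exceeds 23.1%; the point concerns the width of the interval only.

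**What to change.** In SAP 4.3, replace 23.1% with a two-sided 95% upper limit computed from the two existing datasets by a method that accounts for clustering by subject, for example a Wilson limit on the effective sample size or a bootstrap that resamples subjects. If a one-sided bound is intended, say so. Name the method and state 12/79. Report the Estimated Inappropriate Shock Rate twice, at the point estimate (15.2%) and at the upper limit, each labelled as such.

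This needs a short recalculation from data that the sponsor already holds and a few sentences in the SAP. The downside is a slightly less favourable upper figure and two numbers to report instead of one.
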